### 3.7 Sample Size/ Power Calculation

This study aims to evaluate the feasibility of measuring patient experience with new data collection methods and the association between new methods and the EHR-defined variables regarding disease severity and healthcare resource utilization, therefore no comparisons or hypothesis testing will be performed. In order to collect adequate information about the feasibility of these new data collection methods, approximately 200 PPD patients will participate in the study (100 in each group COPD and asthma). If we assume a dropout rate of at most 25%, we will have complete data on at least 150 patients, which will be sufficient to address feasibility of the new collection methods in two different cohorts. In addition, since this is a pilot study to assess feasibility of an interventional study that would use the data capture methods, a formal power calculation is not required.

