Sample Size and Power	
This study aims to evaluate the patient experience with new data collection methods and the association between new methods and the EHR-defined variables regarding disease severity and healthcare resource utilization, therefore no comparisons or hypothesis testing will be performed. In order to collect adequate information about the feasibility of these new data collection methods, approximately 200 PPD [redacted] patients from the integrated delivery network (IDN) will participate in the study (100 in each group COPD and asthma). If we assume a dropout rate of at most 25%, we will have complete data on at least 150 patients, which will be sufficient to address feasibility of the new collection methods in two different cohorts. In addition, since this is a pilot study to assess feasibility of an interventional study that would use the data capture methods, a formal power calculation is not required.

Limitations	
Participants included in this study will be selected from among those within the PPD [redacted] IDN, therefore may not be representative of a sample of all COPD and asthma patients from the US. There will likely be a selection bias based on which patients are willing to participate in a study with multiple devices and due to established inclusion/exclusion criteria. Medication use and activity will be monitored using sensors so there is a risk that the patient's behavior may be altered.

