### 2.2 Specific Objectives

- To evaluate how representative the consented, study population is when compared to the eligible population.
- To develop a monitoring dashboard for integration of data from various devices
- To evaluate patient experience, data quality and consistency with novel, patient-data collection methods:
  - Mobile spirometry
  - Sensor for monitoring rescue medication use
  - Sensor for monitoring maintenance medication use
  - Physical activity monitor
  - Electronic patient reported outcomes (ePROs) – monthly CAT (COPD cohort), ACT (asthma cohort)
    - monthly PROactive – using the C-PPAC
    - For COPD only: EXACT PRO daily symptoms [ERS-COPD]
- To assess the relationships between EHR-based healthcare utilization (ambulatory care visits and hospitalizations for COPD or asthma exacerbations) and lab measures (specified below) with patient data remotely collected via methods outlined in previous bullet, for example.
  - EHR spirometry
  - Blood WBC, eosinophils, neutrophils (number and %)
  - Other blood biomarker samples if available (e.g. fibrinogen, CRP, periostin, sRAGE etc)

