#### **Inclusion Criteria for COPD cohort:**

To be eligible to participate in this study, a subject must meet all of the following criteria:

- Provide signed and dated informed consent form.
- Be willing to comply with all study procedures and be available for the duration of the study.
- Age  $\geq$  40
- Diagnosed with COPD, defined as COPD listed on the patient's problem list and one of the following:
  - At least one inpatient hospitalization with a COPD diagnosis listed as the primary or secondary diagnosis (J41.x, J42.x, J44.x [chronic bronchitis], J43.9 [emphysema] or J44.9 [Chronic obstructive pulmonary disease, unspecified]) in the last 12 months OR
  - At least one emergency room encounter with a COPD diagnosis (J41.x, J42.x, J44.x, J43.9, J44.9) listed as the primary or secondary diagnosis in the last 12 months OR
  - At least two encounters of any combination of the following (each must be a distinctly different event with different dates of service):
    - an outpatient encounter with a diagnosis of COPD exacerbation (J44.1), Acute bronchitis (J20.x), or bronchitis (J40) listed as the primary or secondary diagnosis in the last 12 months, OR
    - an urgent care encounter with a COPD diagnosis (J41.x, J42.x, J44.x, J43.9, J44.9) listed as the primary or secondary diagnosis in the last 12 months
- At least one order for an inhaled COPD medication during the prior year

- 12+ months of data available in the integrated EHR data prior to date of screening

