#### **Inclusion Criteria for Asthma cohort**

- Provide signed and dated informed consent form.
- Be willing to comply with all study procedures and be available for the duration of the study.
- Age  $\geq$  18
- Diagnosed with asthma, defined as asthma listed on the patient's problem list and one of the following:
  - At least one inpatient hospitalization with an asthma diagnosis (J45.x) listed as the primary or secondary diagnosis in the last 12 months OR
  - At least one emergency room encounter with an asthma diagnosis (J45.x) listed as the primary or secondary diagnosis in the last 12 months OR
  - at least two urgent care encounters, with different dates of service, with an asthma diagnosis (J45.x) listed as the primary or secondary diagnosis in the last 12 months OR
  - At least three or more prescriptions or prescription refills in the past 12 months for any combination of the following: an inhaled glucocorticoid with or without a second controller (Montelukast, Theophylline, a long-acting beta agonist [LABA] alone), or a combination drug with a LABA and an inhaled glucocorticoid
- 12+ months of data available in the integrated EHR data prior to date of screening

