#### **Exclusion Criteria (screening question) for COPD cohort**

- Inability/Unwillingness to use the required devices, or
- Inability to read and understand English

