## Appendix 1. Schematic of a Prospective Study:

Clinic Visit 1  
Day 1

- Obtain informed consent
- Screen potential participants by inclusion and exclusion criteria
- Demonstrate devices
- Baseline data collection

During the 6-  
month study  
period

- Perform mobile spirometry weekly
- Wear the activity monitor daily
- Complete the diary card daily (for COPD subjects)
- Complete the CAT/ACT monthly
- Attach sensors to rescue and maintenance inhalers (where appropriate)

Clinic Visit 2  
Month 6

- Exit Interview
- Retrieval of devices

CONFIDENTIAL

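### Does the single figure of 150 completers in Section 3.7 need a separate count for each of the two inhaler sensors?

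*Combined protocol and SAP*

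**What the plan says.** Section 3.7 plans about 200 patients, 100 with COPD and 100 with asthma. The synopsis, under Sample Size and Power, gives the same basis: "If we assume a dropout rate of at most 25%, we will have complete data on at least 150 patients". Section 3.7 expects "complete data on at least 150 patients, which will be sufficient to address feasibility of the new collection methods in two different cohorts". It adds that nothing will be compared or tested, and that a pilot needs no formal power calculation.

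Section 2.2 lists five collection methods: mobile spirometry, a rescue-inhaler sensor, a maintenance-inhaler sensor ("Sensor for monitoring maintenance medication use"), an activity monitor and ePROs. Section 3.6 includes rescue and maintenance medication use among the endpoints.

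Appendix 1 qualifies the sensors and no other device: "Attach sensors to rescue and maintenance inhalers (where appropriate".

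Eligibility (Section 3.2.1.1) bears on inhalers as follows.
- COPD cohort: "At least one order for an inhaled COPD medication during the prior year", with the class of medication left open.
- Asthma cohort, encounter routes: a hospitalization, two urgent care encounters, or "At least one emergency room encounter with an asthma diagnosis (J45.x) listed as the primary or secondary diagnosis in the last 12 months". None of these mentions an inhaler.
- Asthma cohort, prescription route: three or more prescriptions built on "an inhaled glucocorticoid with or without a second controller" or an inhaled combination product. No rescue inhaler is required.

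Both cohorts exclude on "Inability/Unwillingness to use the required devices", and the protocol does not say which devices are required.

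**The concern.** One pooled number is offered for all the new methods, yet two of the five can be used only by patients who have the matching inhaler. A COPD patient could qualify on a rescue inhaler alone or a maintenance inhaler alone. An asthma patient could qualify through an emergency visit with no inhaler prescription on record. Neither dropout nor complete data is defined, so a reader cannot tell whether the 25% allowance also covers patients who never had a sensor fitted.

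The inhaler mix is fixed by who enrols, and later analysis cannot restore it. The study could recruit its 100 per cohort and still have few users of one sensor in one cohort. The feasibility conclusion for that sensor would then be weak, and so would the Spearman correlations of its data with EHR utilization (Sections 2.2 and 4).

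**Working it through.** **Inputs.** Enrolment of 200 (100 per cohort) and dropout of at most 25% come from Section 3.7. The share *a* of patients to whom a sensor applies is not in the documents, so 90%, 75%, 60% and 40% are assumptions. Dropout is assumed equal in both cohorts and unrelated to inhaler type.

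**The plan's own figure.** 200 × (1 − 0.25) = 150, or 100 × 0.75 = 75 per cohort. It reproduces.

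**Completers behind one sensor.** Per cohort this is 75*a*, and pooled 150*a*. For scale, the table adds two per-cohort precision measures:
- the 95% half-width for a yes/no outcome at an assumed 50%, which is 98/√n percentage points;
- the 95% interval for an assumed Spearman correlation of 0.30, from Fisher's z with SE = √[(1 + 0.30²/2)/(n − 3)].

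| Share *a* | Pooled | Per cohort | Half-width (points) | Interval for 0.30 |
|---|---|---|---|---|
| 100% | 150 | 75 | 11.3 | 0.07 to 0.50 |
| 90% | 135 | 67.5 | 11.9 | 0.06 to 0.51 |
| 75% | 112.5 | 56.25 | 13.1 | 0.03 to 0.53 |
| 60% | 90 | 45 | 14.6 | 0.00 to 0.55 |
| 40% | 60 | 30 | 17.9 | −0.08 to 0.60 |

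Because 25% is a stated maximum, these counts are the low end as far as dropout goes.

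**If 150 were required for each sensor.** The largest tolerable dropout would be 1 − 150/(200*a*): 16.7% at *a* = 90% and 0% at *a* = 75%. This bites only if 150 is a requirement per method.

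**Is it a requirement per method?** Section 2.2 gives CAT and the daily symptom diary to the COPD cohort only, and ACT to the asthma cohort only. Under the plan's own assumptions each of these rests on about 75 completers. No patient can supply every stream, so 150 cannot mean 150 patients with all of them. The only workable reading is 150 patients complete on whatever applies to them. On that reading the qualifier in Appendix 1 and the count in Section 3.7 do not conflict.

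**Device exclusion.** It concerns inability or unwillingness to use devices, not prescriptions. A patient without a maintenance inhaler can accept every device that applies, so this exclusion can stand beside the qualifier in Appendix 1.

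**Is a smaller number inadequate?** The documents set no feasibility threshold, precision target or test. None of the rows can be declared too small against anything in the plan.

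**The case for a change.** The strongest case for acting is that inhaler mix is settled at enrolment. The SAP can define a denominator, but it cannot supply patients. Section 3.7 does assert sufficiency for the methods, and calling the study a pilot does not produce the missing sensor count. Section 4 lists no sensor-measured medication-use analysis; its only inhaler count is of albuterol inhalers prescribed. A count from the EHR data pull in Section 3.3.1, one extra field at Visit 1 and a reworded sentence would cost little.

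Most of the facts here stand: the sensor shares are unstated, the required devices are undefined, and a sentence giving the expected number per method would read better. Three things limit the weight of the case.
- Sensor data flow directly to the study database (Section 3.5) and a monitoring dashboard is planned (Section 2.2). The number transmitting by sensor should be visible, although this does not show who was eligible for one.
- A count from the data pull covers one of three recruitment methods. Section 5 expects patients willing to take part to be a selected group, so the count may not predict the enrolled mix.
- The only proposal that would alter the numbers is a minimum per sensor during recruitment. No threshold exists from which to derive it, and steering enrolment by inhaler would select the sample on inhaler use while Section 2.2 asks how representative that sample is. How many EHR-recruited patients can use each sensor is itself a feasibility result.

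**Conclusion.** The observation is accurate, but it does not call for a change. The 150 is correctly calculated as a pooled retention figure, and it is not a number for any single method. Each sensor will rest on 150 times the share of patients with the matching inhaler, just as CAT, ACT and the COPD diary each rest on about 75.

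The possible loss depends entirely on assumed shares. At 90% the per-cohort half-width moves only from 11.3 to 11.9 points; at 40% it reaches 17.9, and a correlation of 0.30 would no longer be distinguishable from zero. The documents do not indicate which case applies. Every COPD patient has an inhaled-medication order and one asthma route is built on inhaled controller prescriptions, so eligibility gives some support for sensor use.

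What is missing is descriptive detail that analysts of a pilot would fill in sensibly: each sensor reported among the enrolled patients to whom it applies, with that number stated. A recruitment minimum is a trade-off against representativeness that the plan can reasonably decline. The conclusion rests on reading completeness as complete on applicable streams, which the cohort-specific questionnaires require. It would change if the sponsor set a feasibility threshold for each sensor.

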#### 4 DATA ANALYSIS CONSIDERATIONS

Descriptive statistics will be presented as frequency and percentages, means and standard deviations, medians and interquartile range (IQR), and for categorical variables, normally distributed and non-normally distributed continuous variables, respectively. Spearman correlations will also be assessed between endpoints. The following will be analyzed over the study period:

- Spirometry (mobile and clinic)
  - Change from baseline in FEV1
- Activity
  - Median/mean steps per day
  - Median/mean daily activity level based on vector magnitude units (VMUs)
- PROactive total score and subdomains Symptoms
- E-RS:COPD symptoms Exacerbations (COPD cohort only)
  - EXACT-defined events
- HCRU
  - Median/mean number of primary care visits for COPD/asthma conditions
  - Median/mean number of secondary care visits (inpatient, urgent care and ED visits) for COPD/asthma conditions
  - Median/mean number of all primary care visits
  - Median/mean number of all secondary (inpatient, urgent care and ED visits) care visits
  - Summary of new prescriptions for any COPD/asthma treatments
  - Number of days in hospital for COPD/asthma
  - Number of albuterol inhalers (adjusted to equivalence of 200 actuations) prescribed
- ePRO
  - Mean change from baseline in CAT (COPD cohort)
  - Mean change from baseline in ACT (asthma cohort)

All analyses will be described in more detail in the full statistical analysis plan.

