#### **3.3.2 Baseline Visit**

A baseline clinic visit will be scheduled with interested patients and a study team member. At the visit, the potential participants will be informed of all pertinent details, risks, and benefits of the study via the study consent form. A study team member will answer any patient questions and patients will be given adequate time to consider participation. Written informed consent will be obtained using the study consent form. After consent, the participant will receive study devices and training on proper use of the devices. Patient vitals including height and weight will be collected by study staff. Participants will complete a baseline questionnaire. Data will be collected remotely from the devices and platforms for six months.

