#### **3.3.3 Six Month Visit**

After six months (+/- 2 weeks), a second visit will be scheduled with the participant and a study team member. At the second visit, the participant will return the study devices and will complete an exit interview to obtain relevant feedback from the patient's perspective on the study. Exit interviews will be performed by PPD personnel.

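### Change in clinic FEV1 is planned without any scheduled clinic spirometry; the EHR values would serve better to check mobile–clinic agreement, and the repeated FEV1, CAT and ACT values to estimate change over time

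*Combined protocol and SAP*

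**What the plan says.** Section 4 lists "Spirometry (mobile and clinic") and beneath it FEV1 change from baseline. The synopsis and Section 3.6 list spirometry without naming a source.

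The schedule contains the following:

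- **Visit 1 (3.3.2):** consent, devices and training, a baseline questionnaire, and "Patient vitals including height and weight will be collected by study staff". No spirometry is named.
- **Visit 2 (3.3.3):** "the participant will return the study devices and will complete an exit interview". No spirometry is named.
- **Appendix 1:** "Perform mobile spirometry weekly" during follow-up, CAT or ACT monthly, and an unspecified baseline data collection on Day 1.
- **Section 2.2:** EHR spirometry is one of the measures to be related to the remotely collected data. No window or frequency is given.
- **Eligibility (3.2.1):** no spirometry is required in either cohort.

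For methods, Section 4 names descriptive statistics and Spearman correlations, and defers detail to a full SAP. Section 3.7 expects at most 25% dropout and says "we will have complete data on at least 150 patients, which will be sufficient" to address feasibility. It also says "no comparisons or hypothesis testing will be performed".

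**The concern.** A change score needs two values per patient, one near the start and one near month 6. For clinic FEV1 the plan secures neither. The patients with both would be those whom usual care tested twice, and that is unlikely to be a random subset. One of the three recruitment routes in 3.3.1 is the pulmonary clinic schedule, so the chance of being tested could plausibly differ by route. A reader of the report could take the result as the cohort's change.

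The EHR values could answer a question the study does ask: whether mobile spirometry gives data of adequate quality. The stated methods do not put them to that use.

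For mobile FEV1, CAT and ACT, the plan collects about 26 weekly sessions and about 6 monthly scores per patient. Section 4 does not say how the series is used or how missing values are handled.

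**Working it through.** **1. The plan's own figure.** Inputs from 3.7: 200 patients, 100 per cohort, dropout at most 25%. 200 × (1 − 0.25) = 150, as stated. With equal dropout that is 100 × 0.75 = 75 per cohort, which is the relevant number for CAT (COPD only) and ACT (asthma only). If all 50 dropouts fell in one cohort, it would keep 100 − 50 = 50.

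**2. Clinic FEV1: analysis against schedule.** Section 4 needs a clinic value at baseline and at follow-up. Sections 3.3.2 and 3.3.3 and Appendix 1 name neither, and eligibility does not require a test. What remains is EHR spirometry (2.2), without a window. The documents give no testing frequency, so the number of patients with two usable values cannot be computed.

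**3. What Spearman correlation can show.** Suppose mobile FEV1 = clinic FEV1 + b for every patient. The ranks are identical, so the correlation is 1 whatever b is. The mean of mobile minus clinic is b. Change within each device does not reveal b either, because (M₂ + b) − (M₁ + b) = M₂ − M₁. Only the paired difference in level shows it.

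**4. Crossing devices.** If a clinic baseline were paired with a mobile follow-up, the expected change would be the true change plus b. Section 4 neither proposes nor excludes this.

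**5. Dropout bias.** With 25% leaving, the full mean is 0.75 × (completers' mean) + 0.25 × (dropouts' mean). The completers' mean therefore differs from it by 0.25 × d, where d is the dropout–completer difference. The documents give no d, so these are assumed values:

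| d | Error in completers-only mean |
|---|---|
| 0.25 SD | 0.06 SD |
| 0.5 SD | 0.125 SD |
| 1.0 SD | 0.25 SD |
| 1, 2 or 3 CAT points | 0.25, 0.50 or 0.75 points |

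For scale, the 95% interval half-width for a mean change is 1.96/√75 = 0.226 SD with 75 patients and 1.96/√100 = 0.196 SD with 100.

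**6. Precision from using all values.** This was calculated per cohort for change at month 6. The assumptions were a baseline plus six monthly values, 25 of 100 leaving evenly over the six intervals, data missing at random, and correlation of 0.5 to 0.9. The documents give no correlation.

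| Correlation structure | Effective n (completers only: 75) | SE ratio = √(75 / effective n) |
|---|---|---|
| Compound symmetry | 81.7 to 82.8 | 0.958 to 0.952 |
| AR(1) | 85.9 to 86.6 | 0.934 to 0.931 |

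The standard error is thus about 4–7% smaller, recovering about 7 to 12 of the 25 patients' worth of information lost. The calculation is for monthly values; weekly FEV1 was not modelled.

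**The case against.** The strongest reply is that this is a feasibility pilot with no hypothesis test, for which "a formal power calculation is not required". Section 2.3 bars device data from serving as a primary clinical outcome measure, and no decision in the documents turns on a mean FEV1 or CAT change. Detail is deferred to a full SAP. That stands, and it limits the weight of the point. It does not remove it: Section 2.2 makes data quality and consistency an objective, and the synopsis aims to scale the methods to interventional trials.

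Four stronger readings are tempting and are not supported:

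- **That clinic FEV1 change cannot be obtained.** Section 2.2 lists EHR spirometry, and 3.5 names EHR records over six months as a prospective source. The Day 1 baseline data collection in Appendix 1 is also unspecified. The data are unsecured, not impossible.
- **That the plan analyses completers only.** Section 4 speaks of the study period as a whole and names no such set. The 150 in 3.7 is a sample-size statement, not an analysis population.
- **That the mobile baseline is badly chosen.** It is undefined, as are the CAT and ACT baselines. That is a clarification for the full SAP.
- **That averaging four early mobile sessions would halve the noise.** With independent errors of SD s, one reading against one gives √2 s = 1.41s. Averaging four at baseline only gives √(1 + 1/4) s = 1.12s, about 21% less. Halving, to √(1/4 + 1/4) s = 0.71s, needs four at both ends. A four-session rule would also keep the early sessions most open to learning effects and could leave early leavers without a baseline.

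**Conclusion.** The point holds in a limited form. Section 4 plans a clinic FEV1 change that no study procedure supports, so as written it would describe a self-selected group of unknown size. The stated association method cannot detect a systematic mobile–clinic difference; this follows from the definition of rank correlation and needs no assumption.

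For the repeated FEV1, CAT and ACT values, the gap is an unspecified method. The main reason to fill it is bias: 0.25 × d if only completers were used, reduced by a repeated-measures model when dropout depends on scores already observed. Dropout that depends on unobserved values would not be corrected. The gain in standard error is small and rests on the assumed correlations and dropout pattern. No sample-size figure is wrong.

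**What to change.** Amend Section 4, or settle it in the full SAP:

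1. **Clinic FEV1 change.** Remove clinic FEV1 from the change analysis. Alternatively, report it only for patients with EHR values in stated windows around Visit 1 and month 6, giving the number who contribute. In either case, compute change within one device only.
2. **Agreement.** Pair each EHR FEV1 with the nearest mobile reading in a stated window, and report the mean difference and limits of agreement with the number of patients.
3. **Change over time.** Summarise mobile FEV1, CAT and ACT with a repeated-measures model on all available weekly or monthly values, separately by cohort, and report dropout by cohort.

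The cost is SAP wording and a little more analysis; no new data collection is needed. The limitation is that agreement can be assessed only in patients with an EHR test, who may not represent the cohort.
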